# 3. Revision History

Document ID - (Document	Description of changes from previous revision	Effective Date
Title) revision X.Y		

# 4. Glossary of terms (Optional)

ADHD = Attention Deficit Hyperactivity Disorder fMRI= functional magnetic resonance imaging NF= Neurofeedback rIFC = right inferior frontal cortex IOPPN = Institute of Psychiatry, Psychology & Neuroscience KCL = King's College London.

# 6. Background & Rationale

Attention deficit hyperactivity disorder (ADHD) children have age-inappropriate problems with inattention, hyperactivity and impulsiveness. The most efficacious current treatment is with psychostimulants, which is effective in 70% of children. However, psychostimulants are associated with long-term adverse effects such as reduced growth, irritability, loss of appetite, tremor, sleep and vegetative disturbances (Greenhill et al., 2001; Jensen et al., 2007). There is also some addictive potential of psychostimulants. Furthermore, nothing is known on the long-term effects of psychostimulants. The last decade has shown an escalating rate of stimulant prescription for ADHD with a net drug costs to the NHS in 2010 of £25m and about £30m for health professional, social and educational time. This escalating prescription rate has raised concerns about the unknown long-term effects on the developing brain. Importantly, recent studies have shown limited long-term effects of psychostimulants beyond 1-2 years, despite the fact that currently stimulants are given to ADHD patients long-term, well into adolescence and adulthood. We and others have shown that the brain adapts to the medication which would explain the limited longer-term effects. In conclusion, adverse effects of psychostimulants, lack of evidence for long-term benefits, and potentially long-term negative effects on brain development make the development of a non-pharmacological treatment for ADHD with no side effects highly desirable to parents, clinicians and patients.

ADHD affects 5-10% of school aged children in the UK. ADHD causes symptoms such as difficulty in focussing attention, impulsiveness and hyperactivity and can seriously impact life, both at home and at school. Underlying their impulsiveness, children with ADHD have problems with self-control, timing and attention. Over the last two decades of brain imaging we and others have shown that these cognitive problems are due to reduced activity in the right inferior frontal part of the brain. Furthermore, one of the main mechanisms of action of stimulant medication, which works in 70% of the cases, is to increase the activity of this brain region. We argue that a therapy that is based on the neuroscience of ADHD, i.e. on the main brain abnormality in ADHD and on the main mechanism of action of stimulant medication, but without side effects, is likely to be successful. We therefore aim to train patients to self-regulate this region of their brain which is underfunctioning, by providing them feedback of their own brain activity.

Patients can be treated by self-regulation of the underlying pathological networks directly, through Neurofeedback (NF). It has been shown that modulating brain function via NF can change behaviour and improve cognitive functions (Birbaumer, et al., 2009). NF is an operant conditioning procedure that allows subjects to achieve volitional and conscious self-control over otherwise unconscious brain activation (and associated processes) mainly through real-time audio/visual feedback. This is achieved by continuously updating subjects with representations of their brain activity on a PC and training them to modulate these representations, usually through trial and error. Changes in the desired direction are rewarded. Since NF can be run as a computer game it is attractive to children. Given that Neurofeedback teaches participants self-regulation of their brain and ADHD is typified by poor self-control, it is the psychiatric disorder where NF has been most applied, using electrophysiology Neurofeedback (EEG-NF).

However, blinded randomised controlled studies of EEG-NF only show trend-level efficacy. Real-time functional magnetic resonance imaging neurofeedback (fMRI-NF) acts more rapidly, presumably due to its superior spatial resolution, allowing more specific targeting of brain regions. Furthermore, it can target deep cortical and subcortical regions such as the rIFC that are most consistently impaired in ADHD. fMRI-NF studies have been promising in other disorders in remediating key neurofunctional substrates and improving

The electronic version of this document is the latest version. It is responsibility of the individual to ensure that any paper material is the current version. Printed material is uncontrolled documentation.

associated behaviours. Our pilot feasibility RT-fMRI-NF study showed that ADHD children can learn to self-regulate rIFC within 11 fMRI-NF sessions of 8.5 minutes each, with significant transfer effects (i.e., after the training they are asked to self-regulate their brain without the NF to show they have learned it) and that this is associated with improved clinical symptoms, cognitive improvements and enhanced rIFC activation during a fMRI task of selfcontrol. However, potential placebo effects cannot be ruled out as we did not include a sham control condition. We therefore plan here a larger and more definite data-driven proof of concept study to test the efficacy of 15 sessions of 7.5 minutes of fMRI-NF of rIFC in 100 children with ADHD, randomised into active and sham control groups, on improving ADHD behaviour, brain function and cognition.

# 7. Trial Objectives and Design

# 7.1 Trial Objectives

# Aim of the study

We plan to test whether fMRI-NF of rIFC will reduce ADHD symptoms and improve their cognitive performance. For this purpose, 100 boys with ADHD aged 10 to 18 years will undergo 4 fMRI scans of 60 min over 2 weeks, where they will be trained to enhance the activity of the rIFC. This will be achieved in a playful way, by playing a videogame of a rocketeer that is connected to their brain activity in rIFC. The goal is for the children to manage to fly the rocketeer into the sky where he will see some planets and asteroids etc, etc. Half of the children will be a control group who will receive a sham NF where they will obtain non-contingent NF from the NF data of one of the active participants. We will test in a well powered study whether fMRI NF in ADHD boys will improve their clinical symptoms, their brain activation and their cognitive problems after the treatment as well as after 6 months to test for longer-term effects. The study will be a first step towards the development of a new, brain-based, non-drug treatment for ADHD which could benefit many young people affected by this condition.

# Objectives of the study:

The proposal is for a suitably powered proof of concept experimental randomized placebocontrolled double-blind trial to test the mechanism and clinical efficacy of rt-fMRI-NF of rIFC compared to sham fMRI-NF in ADHD children.

#### 7.1.1 Primary endpoints

1) ADHD symptoms as measured on the ADHD-Rating Scale (ADHD-RS). (Dupaul et al. 1999).

2) Monotonic increase in inferior frontal lobe activation across the 14 neurofeedback sessions in the active group.

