# 7.2 Trial Design

Double-blind, parallel-group, randomised placebo-controlled trial.

We will test the superiority of the real-time fMRI neurofeedback of rIFC over the sham-NF.

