The active group will be trained to upregulate right inferior frontal lobe activation throughout 14 RT-fMRI-NF runs (7.5 min each, 2-5 sessions per scan), totalling 4 fMRI sessions of 60 minutes over two weeks. In order to prove specificity of NF effects, the control group will have the exact same procedure, but will obtain non-contingent NF from the NF data of one of the active participants.

6. NF sessions (60 min) will consist of 4 runs of each of six activation (upregulation) blocks (40s each), separated by 7 baseline blocks (relaxation/no upregulation), starting and ending with a baseline block (ABABABABABA). The fMRI interface system (provided by [name], Laureate Institute for Brain Research, USA) transfers the images from the MRI

scanner to an external workstation as soon they are reconstructed. Images are then preprocessed using AFNI (afni.nimh.nih.gov/afni), which has built-in real-time capacities. An image mask composed of preselected regions of interest (ROIs) is then applied to the preprocessed images in order to extract the mean neural activity in each selected region. As a new brain volume is acquired every repetition time (2s in this study), AFNI calculates a new set of values for each ROI. The values for each ROI are then sent to a second PC, where they are combined to generate a running time-series for the feedback signal. Finally, this feedback signal is displayed within the scanner in a child-friendly manner. We will present as feedback to the participants their brain activation of rIFG (sham-feedback in controls), using a graphical representation of a rocketeer moving towards the sky, passing through clouds, and ultimately reaching some planets every time they managed to increase the activation of the target region.

Participants cannot easily verbalise the most efficient strategies for successful NF and it is hence more efficient to let participants find their own strategy rather than prescribing one (Birbaumer et al., 2009). The activation will be evaluated in real-time, after each fMRI acquisition, by using the latest reconstructed dataset, i.e. the brain activation during the last 2 seconds.

7. After the last session, the children will be asked to do again the computerised tests of attention, inhibition and timing to test whether they have improved in these skills after the training. The parents also will have to fill in the clinical questionnaires and the side effects scale.

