# 14.1 Sample Size

100 ADHD adolescents will be enrolled in the study, randomised into the fMRI-NF of rIFC (N = 50) and the sham NF (N = 50).

The estimates of a clinically relevant effect size were calculated from our IOPPN pilot study on fMRI-NF in ADHD adolescents using the exact same outcome measures. ES for clinical efficacy in our pilot study was around 0.6. For a mean ES of 0.6 and a power of 80% with a p < 0.05, we would need 45 children in each group. We hence powered the study to include 50 children in each group accounting for a generously estimated potential drop-out rate of up to 10%. Our pilot study was well tolerated by ADHD children who liked the Neurofeedback "game" and we had a drop-out rate of only 5%, which is lower than the 6-10% drop-out rate we have had for studies of repeated fMRI scans under several medication conditions.

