#### 14.3 Analysis

A description of the statistical methods to be employed, including timing of any planned interim analyses should also be provided The level of significance that is to be used in each trial analysis must be stipulated, together with the procedure(s) for accounting for any missing, unused, and spurious data. Procedures for reporting any deviation from the original statistical plan should be described and justified. The data set for any analysis must be clearly stipulated (e.g. "all subjects", "randomised subjects", "intent to treat") and the population(s) should be clearly defined. Define the trial stopping rules if appropriate.

For all analyses, repeated measures ANOVAs will be conducted with TIME as within-subject factor and GROUP as between subject factor. Supplementary analyses may include parametric correlation analyses (for example Pearson's correlation tests).

The named researchers have substantial and proven experience in these types of analyses, having published and taught extensively.

For missing data, imputations will be used. The individual estimates from the multiply-imputed datasets will then be used to calculate a combined estimate by applying Rubin's Rules [Little and Rubin, 2002].

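### Primary endpoint 2 (rIFC activation) is defined as a rise in the active arm only, which conflicts with the stated comparison with sham and with the TIME by GROUP analysis

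*Protocol*

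**What the plan says.** Protocol Section 7.1.1 lists two primary endpoints. The first is the ADHD-RS. The second is "Monotonic increase in inferior frontal lobe activation across the 14 neurofeedback sessions in the active group". The synopsis gives the corresponding primary objective as greater rIFC activation over the 14 sessions, again without a comparator.

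Other sections describe a comparative trial:

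- Section 7.1, under the objectives, says the trial is "to test the mechanism and clinical efficacy of rt-fMRI-NF of rIFC compared to sham fMRI-NF in ADHD children".
- Section 7.2 says "We will test the superiority of the real-time fMRI neurofeedback of rIFC over the sham-NF".
- Section 11, step 5, explains the sham arm: "In order to prove specificity of NF effects, the control group will have the exact same procedure".
- Section 14 applies repeated measures ANOVA, with TIME within and GROUP between subjects, to behavioural and fMRI data. Section 14.3 repeats this without exception: "For all analyses, repeated measures ANOVAs will be conducted with TIME as within-subject factor and GROUP as between subject factor".

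Neither Section 14 nor Section 14.3 says which term of that model decides the second primary endpoint.

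**The concern.** The sham children attend the same visits, do the same runs in the same scanner and see the same game. Effort, practice, growing ease in the scanner or expectation could raise activation during upregulation in both arms. An endpoint that asks only whether the active arm rises cannot separate such a shared rise from an effect of contingent feedback.

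This is the only primary endpoint that addresses mechanism. The Background (Section 6) concedes that placebo effects could not be excluded in the pilot because it had no sham condition. A one-arm criterion would bring the same uncontrolled inference into a randomised trial that has the data to avoid it. Two analysts could also reach opposite conclusions from the same data, one following Section 7.1.1 and the other the GROUP factor in Section 14.3.

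**Working it through.** **1. The protocol's own sample size.** Section 14.1 says: "For a mean ES of 0.6 and a power of 80% with a p < 0.05, we would need 45 children in each group". For two groups at two-sided 5%, the normal approximation is n = 2(1.960 + 0.842)² / 0.6² = 2 × 7.85 / 0.36 = 43.6, so 44 per arm. The exact two-sample t test gives 44.6, so 45. Allowing for 10% dropout, 45 / 0.90 = 50. The stated figures reproduce. A one-sided test would need 35 and does not match. This is a two-group calculation for a clinical outcome ("ES for clinical efficacy in our pilot study was around 0.6"). The protocol gives no effect size for rIFC activation.

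**2. What the wording allows if the arms do not differ.** The size of a shared rise is not in the documents, so a range is assumed. Let δ be the mean slope across runs divided by the SD of the individual children's slopes, with the same δ in both arms, so that the true active-minus-sham difference is zero. A linear slope stands in for a monotonic rise, which the protocol does not define operationally.

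An active-only test is a one-sample t test on n slopes, with noncentrality δ√n on n − 1 degrees of freedom. For example, δ = 0.5 and n = 50 give 0.5 × 7.07 = 3.54.

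| Assumed common slope δ | Active-only test significant, n = 50 | n = 45 | Between-arm test significant |
|---|---|---|---|
| 0 | 5% | 5% | 5% |
| 0.2 | 28% | 26% | 5% |
| 0.3 | 55% | 50% | 5% |
| 0.5 | 93% | 91% | 5% |

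A simulation of 20,000 trials at δ = 0.5 agrees. The active-only test was significant in 93.2% (n = 50) and 90.7% (n = 45), and the between-arm test in 5.4% and 5.0%.

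**3. Power of a between-arm endpoint.** For a true slope difference Δ in SD units, the noncentrality is Δ√(n/2). With n = 45, √22.5 = 4.74.

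- Δ = 0.6: noncentrality 2.85, power 80%.
- Δ = 0.5: noncentrality 2.37, power 65%.

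**4. Which term decides.** In a TIME by GROUP model, the TIME main effect can also be significant when both arms rise together. Only the interaction, or a trend contrast within it, compares the arms. Prescribing the model without naming the term therefore does not settle the endpoint.

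**5. The number of runs.** Section 7.1.1, the synopsis, Section 8.1 and Section 11 (step 5) give 14. The Background gives 15, and the visit-by-visit schedule in Section 8.1 adds up to 2 + 5 + 5 + 3 = 15. The endpoint is a trend across these runs, so the count is part of its definition.

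**The case against.** The strongest reply is that Section 7.1.1 names an outcome and not a test. The tests are in Sections 14 and 14.3, which put a GROUP factor into the fMRI analysis and into all analyses. On that reading the active-group phrase only says where the rise is predicted, and sham will be compared as a matter of course. This part of the reply stands: a reader might infer that the plan tests only within the active arm and throws away the randomised control, and the documents do not support that. The stated intent is comparative, and the general model contains a comparison with sham.

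It does not remove the conflict. The endpoint definition is confined to one group, a GROUP factor cannot be fitted to an endpoint so confined, and no sentence says that the interaction takes precedence. A statistical analysis plan may name the term, but the protocol has already fixed the endpoint in one-arm wording.

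Three further points are fair:

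- The percentages rest on assumed slopes. With no shared rise, the active-only test keeps its 5% error rate.
- Slow scanner drift is a weak explanation, because upregulation blocks alternate with rest blocks and contrasting the two removes much of it. Practice, effort and habituation remain.
- The clinical conclusion does not depend on this endpoint. Section 12 names the ADHD-RS as the primary efficacy measure. Stop-task activation is listed without restriction to one arm, but only as a secondary endpoint.

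**Conclusion.** The point holds as an inconsistency in a primary endpoint. The definition in Section 7.1.1, echoed in the synopsis, leaves out the comparison with sham that the objectives, the superiority statement, the rationale for the sham arm and the general ANOVA all call for. As worded, it can be satisfied with no difference between the arms. That conclusion follows from the wording and needs no assumed number.

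The size does depend on assumptions. For a common slope of 0.2 to 0.5 SD, the active-only criterion would be met in 28% to 93% of trials at 50 per arm, or 26% to 91% at 45, against 5% for a between-arm test. A reader might take the upper figure as the trial's false-positive rate. It is not: it applies only if a shared rise of that size exists and the active-only linear-slope test is the one used to declare success, and the documents establish neither.

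**What to change.** Redefine primary endpoint 2 as the active-minus-sham difference in the trend of rIFC activation (upregulation minus rest) across neurofeedback runs. State that the deciding term is the GROUP by run trend contrast within the TIME by GROUP model of Sections 14 and 14.3, tested two-sided. Say whether the trend is linear, since this would replace the undefined monotonic rise. Keep the active-arm trend as supportive only.

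Align the synopsis, Section 7.1.1 and Section 14.3 with this definition. Reconcile the run count (14 or 15) wherever it appears.

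The cost is a change of text in those sections. The sham runs are already scheduled, so no new data are needed. The real price is power: at 45 per arm the contrast has about 80% power for a slope difference of 0.6 SD and 65% for 0.5 SD. The protocol should state the slope difference it expects, because the 0.6 in Section 14.1 belongs to the clinical outcome.

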# 7.1.2 Secondary endpoints

- 1) The ADHD Index of the Conners Parent Rating Scales (CPRS).
- 2) Stop fMRI task performance and related brain activation.
- 3) A cognitive task battery we have developed for ADHD that measures key functions including inhibition, attention, timing and motivation and which lasts 30min (Rubia, Smith, & Taylor, 2007).
- 4) Other clinical measures:
  - a. the Affective Reactivity index (ARI) (Stringaris et al., 2012) (2min)

- b. the Columbia Impairment Scale (CIS) (Bird, et al., 1003) (5min)
- c. The Mind excessive wandering scale (MEWS) (Mowlem et al., 2016)
- 4) Side effect scale (Hill & Taylor, 2001). (5min)

5) Long-term effects will be assessed 6 months after training in the primary outcome measure (ADHD-RS for parent-ratings), the ARI, the MEWS and in the performance on the cognitive task battery.

# 7.2 Trial Design

Double-blind, parallel-group, randomised placebo-controlled trial.

We will test the superiority of the real-time fMRI neurofeedback of rIFC over the sham-NF.

# 7.3 Trial Flowchart

Please include a time/event matrix (flow chart) of trial procedures and stages. This desirable is it is particularly useful for determining activities involved during each clinic visit (e.g. blood tests or scans, treatment, diary completion, adverse event monitoring, physical examination etc).

	Baseline	Visit A NF-	Visit B NF-	Visit C NF-	Visit D NF-	Endpoint	6-month Follow-
Date		training	training	training	training		~P
Start / End time							
		Researche	r administe	red			
Eligibility checklist							
K-SADS							
DSM-5 ADHD criteria							
NF Scan Training Form							
		Self-ad	Iministered				
Background Information (P)							
Edinburgh Handedness (C)							
SCQ (P)							
Medication form (P or C)							
Conners 3-PL (P)							
ADHD-RS (P)							
CIS (P)							
WREMB-R (P)							
ARI (C)							
ARI (P)							
MEWS (P)							
Side effects (P)							
Adverse effects (P)							
NF Questionnaire (C)							
NF Effectiveness questionnaire (P)							
Mood before & during NF (C)							
Blindness form (P and C)							
Neurocognitive measures							
WASI (40-60min)							
Go-no go task (5min)							
Continuous performance task (8min)							
Interference inhibition (Simon Task) (5min)							

Wisconsin Card Sort Task (5min)				
Working memory (6min)				
Vigilance task (5min)				
fMRI Stop task (6min)				
	F	orms		
Consent form child				
Consent form parent				
MRI safety form				
MRI request form				
Receipt of payment				

Figure 1. Schematic overview of the design of the rtfMRI-NF study. ADHD-RS, Attention Deficit Hyperactivity Disorder-Rating Scale; CIS, Columbia Impairment Scale; CPRS-R, Conners' Parent Rating Scale - Revised; K-SADS-PL, Kiddie-SADS-Present and Lifetime Version; MARS, Maudsley Attention and Response Suppression task battery; NF, Neurofeedback; SCQ, Social Communication Questionnaire (Lifetime); Wechsler Abbreviated Scale of Intelligence, 2nd Edition (WASI-II); WREMB-R, Weekly Rating of Evening and Morning Behavior-Revised; ARI, Affective Reactivity index; MEWS; Mind Excessive Wandering Scale. Adapted from Alegria et al., 2017, Human Brain Mapping, in press.

# 8. Trial Intervention

# 8.1 Therapy/Intervention Details

Participants will be scanned 4 times in a new GE MR750 3T scanner (General Electrics Milwaukee, USA) for 60 min. Patients will be randomly allocated to active (N = 50) or control groups (N = 50), stratified by age and medication status. The active group will be trained to upregulate right inferior frontal lobe activation throughout 14 fMRI-NF sessions (7 min 30sec each, 2-5 sessions per scan), totalling 4 fMRI scan hours over two weeks. The first of the 4 visits will contain the 6min fMRI task and 2 NF sessions. Visit 2 and 3 will contain 5 NF sessions each followed by a transfer session without feedback. Visit 4 will contain 3 NF sessions, the Stop fMRI task, and a transfer session. The control group will have the exact same procedure, but will obtain non-contingent NF from the NF data of one of the active participants.

NF sessions (1hr) will consist of either 2 (visit 1) or 5 (visit 2-3) and 3 (visit 4) runs of each of six activation (upregulation) blocks (40s each), separated by 7 baseline blocks (relaxation/no upregulation, 30s), starting and ending with a baseline block (ABABABABABA). The RT-fMRI interface system (provided by [name], Laureate Institute for Brain Research, USA) transfers the images from the MRI scanner to an external workstation as soon they are reconstructed. Images are then pre-processed using AFNI (afni.nimh.nih.gov/afni), which has built-in real-time capacities. An image mask composed of pre-selected regions of interest (ROIs) is then applied to the pre-processed images in order to extract the mean neural activity in each selected region. As a new brain volume is acquired every repetition time (2s in this study), AFNI calculates a new set of values for each ROI. The values for each ROI are then sent to a second PC, where they are combined to generate a running time-series for the feedback signal. Finally, this feedback signal is displayed within the scanner in a child-friendly manner. We will present as feedback to the participants their brain activation of rIFC, using a graphical representation of a rocketeer that flies up in the sky (with increasing activation) or does not move (no activation/rest) and we will ask the subjects to try to make the rocketeer fly, thus increasing their brain activation in the ROIs. The rocketeer movie is done by a professional videogaming artist and is highly engaging and fun. Participants cannot easily verbalise the most efficient strategies for successful NF and it is hence more efficient to let participants find their own strategy rather than prescribing one (Birbaumer et al., 2009). The activation will be evaluated in real-time, after each fMRI acquisition, by using the latest reconstructed dataset, i.e. the brain activation during the last 2 seconds.

